7.1.6.2 Incomplete Dates

If the onset date of AE is incomplete and the AE stop date is not prior to the first dosing date of study treatment, then the month and year (or year alone if month is not recorded) of onset determine whether an AE is treatment emergent. The event is considered treatment emergent if both of the following 2 criteria are met:

- The AE onset/severity worsened is the same as or after the month and year (or year) of the first dosing date of study treatment, and
- The AE onset/severity worsened is the same as or before the month and year (or year) of the last dosing date of study treatment

An AE with completely missing onset and stop dates, or with the onset date missing and a stop date later than the first dosing date of study treatment, will be considered to be treatment emergent. In addition, an AE with onset date missing and incomplete stop date with the same or later month and year (or year alone if month is not recorded) as the first dosing date of study treatment will be considered treatment emergent.

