## 7 ADVERSE EVENTS AND SERIOUS ADVERSE EVENTS

The following definitions of terms are guided by the International Conference on Harmonisation and the U.S. Code of Federal Regulations [21 CFR 312.32] and are included herein.

An adverse event (AE) is any untoward medical occurrence associated with the use of a drug in humans, whether or not considered drug related.

AEs include, but are not limited to:

- Any symptom or condition not previously reported by the subject (medical history).
- An exacerbation of a pre-existing symptom or condition.
- A significant increase in frequency or intensity of a pre-existing episodic event or condition.
- A drug interaction.
- A condition first detected or diagnosed after study drug administration even though it may have been present prior to the start of the study.

An AE does not include:

- Medical or surgical procedures (e.g., surgery, endoscopy, tooth extraction, or blood transfusion); the condition that leads to the procedure is an adverse event (e.g., bleeding esophageal varices, dental caries).
- Overdose of either study drug or concurrent medication without any clinical signs or symptoms.

All identified AEs after signing of informed consent until 84 days after last study drug dose must be recorded and described on the appropriate non-serious or serious AE page of the eCRF. If known, the diagnosis of the underlying illness or disorder should be recorded, rather than individual symptoms.

Suspected adverse reaction means any AE for which there is a reasonable possibility that the drug caused the AE. For the purposes of safety reporting, ‘reasonable possibility’ means there is evidence to suggest a causal relationship between the drug and the AE. A suspected adverse reaction implies a lesser degree of certainty about causality than adverse reaction, which means any AE caused by a drug.

An adverse reaction is any AE caused by a drug. Adverse reactions are a subset of all suspected adverse reactions for which there is reason to conclude that the drug caused the event.

An AE or suspected adverse reaction is considered “serious” if, in the view of either the Investigator or sponsor, it results in any of the following outcomes:

- Death
- A life-threatening adverse event

- Inpatient hospitalization or prolongation of existing hospitalization
- A persistent or significant incapacity or substantial disruption of the ability to conduct normal life functions
- A congenital anomaly/birth defect

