### **9.2.7 Evaluation of Safety Parameters**

#### **9.2.7.1 Adverse Events and Adverse Events of Special Interest**

All AEs will be coded using most current version of Medical Dictionary for Regulatory Activities (MedDRA). All reported adverse events will be assigned to the SOC and PT according to MedDRA. The number and percentage of subjects reporting AEs (all, serious, related) will be

tabulated by overall and treatment. AEs will be summarized by SOC and PT. AEs will also be summarized by relationship to the study drug, seriousness, and severity.

A treatment-emergent AE (TEAE) will be defined as an AE that began or worsened on or after the first treatment dose. AEs recorded prior to the first infusion of study treatment will be considered non-treatment-emergent.

All reported AEs (treatment-emergent or not) will be listed. Only TEAEs will be summarized.

AEs of special interest including infections, acute infusion reaction (within 1 hour of completion of infusion), and peri-infusion reaction (within 24 hours of completion of infusion) will be summarized based on a pre-specified MedDRA list.

AEs occurring in subjects who are considered immunogenicity positive will also be summarized.

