7.1.6 TREATMENT EMERGENT ADVERSE EVENTS

7.1.6.1 Definition of Treatment Emergent Adverse Events

Treatment Emergent Adverse Events (TEAE) are defined as following:

- AE onset date \geq 1st study treatment date; or
- AE worsened on or after the 1st study treatment date

AEs recorded prior to the first infusion of study treatment will be considered non-treatment-emergent. All reported AEs (treatment-emergent or not) will be listed. Only TEAEs will be summarized.

AEs of special interest including infections, acute infusion reaction (within 1 hour of completion of infusion), and peri-infusion reaction (within 24 hours of completion of infusion) will be summarized based on a pre-specified MedDRA list.

AEs occurring in subjects who are considered immunogenicity positive will also be summarized.

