7.1.7 SUMMARIES OF ADVERSE EVENTS

Treatment Emergent (TE) AEs will be summarized based on the Safety Analysis Set by treatment period and post-treatment period, separately.

Summary tables will be presented to provide the number and percentage of subjects experiencing any AEs, any severe AEs, any drug-related AEs, any SAEs, any drug-related SAEs, and any AEs leading to study drug interruption or discontinuation.

In addition to the above summary table, summary tables and listings of adverse events listed below will be provided.

- Summary of TEAEs by SOC and PT
- Summary of TEAEs by SOC, PT and Max Severity
- Summary of Severe (CTCAE Grade \geq 3) TEAEs by SOC and PT
- Summary of Related TEAEs by SOC and PT
- Summary of TESAEs by SOC and PT
- Summary of Related TESAEs by SOC and PT
- Summary of AEs in Follow-up by SOC and PT
- Listing of All AEs
- Listing of TESAEs or Death
- Listing of TEAEs Leading to Study Drug Interruption or Discontinuation

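### An AE dated only to a month after the last-dose month is not treatment-emergent under SAP 7.1.6.2, although the same AE with a full date is

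*SAP*

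**What the plan says.** For complete dates, SAP 7.1.6.1 counts an AE as treatment-emergent if it starts on or after the first treatment date, or if the "AE worsened on or after the 1st study treatment date". Protocol 9.2.7.1 says the same: "an AE that began or worsened on or after the first treatment dose". Neither sets an end date. SAP 7.1.6.1 adds "Only TEAEs will be summarized".

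For incomplete onset dates, SAP 7.1.6.2 states: "The event is considered treatment emergent if both of the following 2 criteria are met". The first criterion is that onset or worsening is not before the month (or year) of first dose. The second is that it is "same as or before the month and year (or year) of the last dosing date of study treatment". An AE whose onset date is wholly missing is handled separately. It counts as treatment-emergent if the stop date is also missing, is later than first dose, or is partial and not before the month (or year) of first dose. That rule has no upper limit.

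Two other places show what the plan intends for events after dosing. Protocol section 7 says "All identified AEs after signing of informed consent until 84 days after last study drug dose must be recorded". SAP 7.1.7 tabulates TEAEs "by treatment period and post-treatment period, separately" and also lists a "Summary of AEs in Follow-up by SOC and PT".

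**The concern.** The same event changes class because the day of onset was not recorded. With a full date, an AE in the follow-up period is a TEAE. With month and year only, it is not, once that month is later than the month of last dose. If nothing is known of the onset but the stop date is after first dose, it is a TEAE again. So knowing the month can make an event less likely to count than knowing nothing about its onset.

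Because only TEAEs are summarised, a misclassified event leaves the overall, serious, severe and related TEAE tables. The proportion of subjects reporting AEs and SAEs is a primary endpoint. The follow-up window also matters for this drug: Protocol 1.4.1 gives a half-life of about 19 days, Protocol 4.5 ties the 12-week follow-up to the long half-life, and infections are an AE of special interest.

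**Working it through.** The plan gives no figure on this point, so there is nothing to reproduce. The check applies both date rules to every onset day in follow-up.

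**Inputs**

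- Upper limit, complete dates: none (SAP 7.1.6.1, Protocol 9.2.7.1).
- Upper limit, partial dates: month, or year, of last dose (SAP 7.1.6.2).
- AE collection: to 84 days after last dose (Protocol section 7).
- Last induction dose Day 71, Week 12 visit Day 85 (Protocol Table 2).
- Assumption: last-dose dates are spread evenly over the 730 days from 1 July 2021 to 30 June 2023, with first dose 70 days earlier. This span contains no 29 February, so one 365-day year gives the same averages.

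**Month and year known, day missing.** Let L be the length of the last-dose month, d the day of last dose and r = L − d the days left in that month. Onset days 1 to r after last dose still qualify; days r + 1 to 84 fail. The failing share is (84 − r)/84.

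- Most: last dose on the last day of a month, r = 0, 84/84 = 100%.
- Least: last dose on the first of a 31-day month, r = 30, 54/84 = 64%.
- Average: mean r = (7 × 465 + 4 × 435 + 378)/365 = 5373/365 = 14.72, where 465, 435 and 378 are L(L − 1)/2 for months of 31, 30 and 28 days. The share is (84 − 14.72)/84 = 82%.

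**Year only known.** With y days left in the year, the share is (84 − y)/84 if y < 84, and 0 otherwise. The average is (84 × 85/2)/(365 × 84) = 3570/30660 = 12%, all of it from follow-up that crosses into a new year.

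**Complete dates.** 0% fail.

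**Inside the induction period.** If Week 10 is the last dose, Days 72 to 85 are the 14 days after it. With the day missing, the failing share is (14 − r)/14 if r < 14, and 0 otherwise. Each month contributes 14 + 13 + … + 1 = 105, so the average is 12 × 105/(365 × 14) = 1260/5110 = 25%, with a range of 0% to 100%.

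**Example.** First dose 10 January 2022 (Day 1), last dose 21 March 2022 (Day 71), Week 12 on 4 April 2022 (Day 85), AE collection to 13 June 2022.

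| Onset as recorded | Class |
|---|---|
| 3 April 2022 (Day 84) | TEAE |
| April 2022 | not a TEAE |
| 2022 | TEAE |
| missing, stop date after first dose | TEAE |

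Here r = 31 − 21 = 10, so 74/84 = 88% of follow-up days fail when the day is missing, as do 4 of the 14 days from Day 72 to Day 85 (29%).

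**After the change.** With the upper limit removed, or moved to 84 days after last dose, 0% of the 84 follow-up days fail, as with complete dates.

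**The case against.** The strongest reply is that little is lost in practice. Partial onset dates should be uncommon, since follow-up visits come every 28 days. Every event stays in the listing of all AEs. SAP 7.1.7 also plans the follow-up AE table, whose title does not restrict it to TEAEs. The affected events begin in a calendar month after last dose, so most would belong in the post-treatment tables rather than the 12-week induction results. For subjects who enter the extension, the last dosing date is later, and no induction event is touched.

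Most of this stands, and it limits the size of the point. It does not remove the conflict. The follow-up table is an uncertain safeguard, because SAP 7.1.6.1 restricts summaries to TEAEs, and the serious, severe and related TEAE tables would lose the events either way. Nor can the limit be defended as deliberately confining partly dated events to the dosing period: fully dated events after dosing count, and SAP 7.1.7 provides for post-treatment TEAEs. The SAP's partial-date rule for concomitant medication (5.4.2) allows 30 days beyond last dose; the AE rule allows none.

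A reader might infer that the whole section errs towards under-counting. It does not. The first criterion admits any AE dated to the month (or year) of first dose, including one that began before dosing, and an AE with both dates missing also counts. Only the second criterion, taken alone, can do nothing but under-count. Nor does every AE without an onset date count; the stop-date conditions must be met.

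**Conclusion.** The partial-date rule is inconsistent with the TEAE definition it is meant to implement, and nothing elsewhere in the documents resolves this. If only the day is missing, about 82% (64% to 100%) of follow-up onset days are misclassified; if only the year is known, about 12%. When Week 10 is the last dose and a month boundary intervenes, part of Days 72 to 85 is lost too. Events in the last-dose month, and year-only events in the last-dose year, are unaffected. The averages rest on evenly spread last-dose dates; the range for a missing day follows from the calendar alone.

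These are shares of days. The documents do not say how many AEs will be partly dated, so the number of events lost is unknown and probably small. A reader might infer a larger effect from the length of follow-up: with last dose at Day 71, follow-up is 84 of 71 + 84 = 155 days, or 54%. That figure is not the share the rule affects, and it applies only when dosing stops at Week 10. With a last dose at Week 50 (Day 351) it is 84/435 = 19%. A reader might also infer that post-dose events vanish from safety reporting. They do not: fully dated events remain TEAEs, and all events are listed. This is a minor but real inconsistency, worth correcting because correction is so cheap.

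**What to change.** In SAP 7.1.6.2, delete the second criterion. Partial dates then follow the same open-ended definition as complete dates. Alternatively, keep an upper limit but set it at 84 days after the last dosing date, which gives agreement across the AE collection period. In either case, assign the event to the treatment or post-treatment period in a separate step, after TEAE status is settled. SAP 7.1.7 does not say how a partly dated event is placed.

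The cost is one line of text, a short period-assignment rule and the matching programming. SAP V02 is marked final, so the change and its rationale should be documented in the clinical study report, as SAP section 1 requires. No data collection changes.

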7.1.7 SUMMARIES OF ADVERSE EVENTS

Treatment Emergent (TE) AEs will be summarized based on the Safety Analysis Set by treatment period and post-treatment period, separately.

Summary tables will be presented to provide the number and percentage of subjects experiencing any AEs, any severe AEs, any drug-related AEs, any SAEs, any drug-related SAEs, and any AEs leading to study drug interruption or discontinuation.

In addition to the above summary table, summary tables and listings of adverse events listed below will be provided.

- Summary of TEAEs by SOC and PT
- Summary of TEAEs by SOC, PT and Max Severity
- Summary of Severe (CTCAE Grade \geq 3) TEAEs by SOC and PT
- Summary of Related TEAEs by SOC and PT
- Summary of TESAEs by SOC and PT
- Summary of Related TESAEs by SOC and PT
- Summary of AEs in Follow-up by SOC and PT
- Listing of All AEs
- Listing of TESAEs or Death
- Listing of TEAEs Leading to Study Drug Interruption or Discontinuation

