
STUDY DESIGN:
	
This is a multi-center, open-label, proof of concept study designed to assess the safety, tolerability, and preliminary efficacy of PRA023 following 12 weeks of induction therapy in subjects with Crohn’s disease (CD). This study will be conducted under the aegis of a Data Monitoring Committee (DMC) and will commence following the demonstration of an acceptable safety profile of PRA023 at a dose of <math>\geq 500</math> mg in the multiple ascending dose study in normal healthy volunteers (Study PR200-101).
 
The study has 4 periods (Screening, IP, OLE and Follow-Up [FU] Period). Following the Screening Period, approximately 50 eligible subjects with moderately to severely active CD will enter the IP to receive PRA023 1000 mg on Week 0/Day 1, followed by 500 mg on Weeks 2, 6, and 10 via intravenous (IV) administration. Subjects who discontinue from the study drug will have a follow-up period of 12 weeks after the last dose.
 
Response at Week 12 will be defined as reduction from Baseline in CDAI of <math>\geq 100</math> points. Non-responders at Week 12 should discontinue from study drug treatment.
 
Subjects who complete the 12-week IP and have responded will have the option to enter OLE, where they will be randomized to either 250 mg IV

	
Q4W or 100 mg IV Q4W until Week 134 Subjects will continue in OLE until they progress, withdraw from the study, study termination, or Week 134.
 
The study is being amended by the Sponsor to extend the OLE period beyond 50 weeks to Week 134 based on emerging safety data in both this study as well as a concurrent double-blind Phase 2 study in ulcerative colitis. The OLE period may be further extended beyond 134 weeks based on emerging safety data in a future amendment.

SAMPLE SIZE:	The study is planned to enroll approximately 50 subjects. The sample size will enable a statistical power of 80%, at 1-sided significance level of 0.025, to test against the null hypothesis of endoscopic improvement rate of 12%, assuming the endoscopic improvement rate for PRA023 is 27%.
SUBJECT TYPE:	Male or female subjects $\geq$ 18 years of age with moderately to severely active CD.
FORMULATIONS:	PRA023 will be supplied in 10 mL vials each containing 500 mg PRA023 (60 mg/mL concentrate for solution for infusion) for IV administration after reconstitution.

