1 INTRODUCTION

This statistical analysis plan (SAP) describes in detail the analyses to be performed for the Induction Period (IP) of the study on the safety, efficacy, and pharmacokinetics of PRA023 in subjects with moderately to severely active Crohn’s Disease(CD). This SAP describes the statistical analysis methods and data presentations to be used in tables, figures, and listings (TFLs) in the clinical study report (CSR) for study PR-200-103. This SAP is based on the study protocol version 3.0.

There will be a primary analysis after all subjects have completed 12-week IP. The analysis will include complete data for the induction period and interim data for the OLE as of the cutoff date for the database lock. Outstanding data queries would have been resolved or adjudicated as unresolvable, and data should have been cleaned and finalized before database lock. Following the database lock after all subjects have completed Induction Period, the primary analysis of the data will be performed.

The SAP will be finalized and approved before 50% of planned subjects enrolled and initiated dosing. Any changes made after the finalization and approval of the SAP will be documented in the CSR with the rationale.

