4 GENERAL CONSIDERATIONS FOR DATA ANALYSES

4.1 REPORTING CONVENTIONS

The following reporting conventions apply generally to tables, listings, and graphs:

- Unless otherwise specified, the baseline value is defined as the last non-missing assessment before the first does of study treatment.
- If the date of interest occurs on or after the first dose date, the study day will be calculated as (date of interest – date of first dose) + 1.
- If the date of interest occurred prior to the first dose date, then study day will be calculated as (date of interest – date of first dose).
- Categorical data will be summarized by treatment group in terms of frequency counts and percentages.
- Continuous variables will be summarized by treatment group using descriptive statistics (the number of subjects (n), mean, median, standard deviation (SD), minimum (Min), and maximum (Max)) of the values at each visit and the change from baseline to each visit, unless specified otherwise.
- Confidence Intervals (CIs) will be presented as 2-sided 95% CIs.
- All mean, median and CI values will be formatted to one more decimal place than the measured values. SD values will be formatted to two more decimal places than the measured value. Min and Max will be formatted to the same number of decimal places as the measured value. The maximum number of decimal places reported shall be four for any summary statistic.
- All percentages will be rounded to one decimal place, unless specified otherwise. The number and percentage of responses will be presented in the form xx (xx.x), where the percentage is in the parentheses.
- Change from baseline is calculated as a post-baseline value minus the baseline value.
- All laboratory data will be reported using standard international units.
- All analysis and summary tables will include the analysis population sample size (ie, number of subjects) in the column headings.

- By-subject listings will be presented for all subjects in the relevant analysis sets, and sorted by treatment allocation, study site (if applicable), Subject ID, date, and visit. Numeric data will be listed to the same number of decimal places as recorded on the eCRF or other data source. Data collected on log forms, such as AEs, will be presented in chronological order within the subject, and age, and sex will be included in the listing, as space permits.

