4.2.2 SAFETY ANALYSIS SET

All subjects who received at least 1 dose of study drug will be included in the safety analysis set. The Safety Analysis Set is the primary analysis set for safety analyses.

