5.3 TREATMENT EXPOSURE

5.3.1 EXPOSURE

Since this is an open-label study, there is no blinding. The site pharmacist(s) or designee will be preparing study drug for infusion. Detailed study drug preparation and handling instructions will be provided to the investigational pharmacist in the Pharmacy Manual.

Total duration of exposure to study treatment during Induction period is defined as the number of days elapsed from date first dose to the date of Week 14 visit for patients who enter OLE, or otherwise, to the date of 4 weeks after last dose or the date of data cutoff for the primary analysis, whichever is earlier. The total duration of exposure to study treatment and total number of infusions received for the IP and OLE will be summarized using descriptive statistics for the Safety Analysis Set.

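### Follow-up adverse event percentages are based on all treated subjects, including those still on PRA023 in the OLE at the cut-off, who have no post-dosing follow-up

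*SAP*

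**What the plan says.** SAP 7.1.7 states that treatment-emergent adverse events "will be summarized based on the Safety Analysis Set by treatment period and post-treatment period, separately". The statistic is a count with a percentage: "Summary tables will be presented to provide the number and percentage of subjects experiencing any AEs" and the other listed categories. The list of tables includes a "Summary of AEs in Follow-up by SOC and PT", with no denominator of its own.

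SAP 4.2.2 defines the set: "All subjects who received at least 1 dose of study drug will be included in the safety analysis set". SAP 4.1 adds: "All analysis and summary tables will include the analysis population sample size (ie, number of subjects) in the column headings". SAP 4.2 defines five sets (screening, safety, full analysis, per-protocol, OLE). None consists of the subjects who entered post-dosing follow-up.

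On who is followed, the Protocol Synopsis says: "Subjects who discontinue from the study drug will have a follow-up period of 12 weeks after the last dose". SAP 3.1 has the matching rule, and SAP Table 2 identifies the post-treatment period with safety follow-up. Week 12 responders may instead continue PRA023 in the OLE, to Week 50 in the SAP (written on protocol version 3.0) and to Week 134 in the current protocol.

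On timing, SAP Sections 1 and 9 place the primary analysis once every subject has completed the 12-week induction period. It includes "interim data for the OLE as of the cutoff date for the database lock".

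**The concern.** A percentage of subjects with a follow-up event describes risk only if the subjects in the denominator could have had one. A subject still being infused in the OLE at the cut-off has not begun post-dosing follow-up, so that subject adds one to the denominator and can add nothing to the numerator.

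The off-drug window is a real part of the safety picture. Protocol 1.4.1 gives a half-life of about 19 days, and Protocol Section 7 has adverse events recorded until 84 days after the last dose. If the treatment and post-treatment summaries both carry the same N of about 50, events will look rarer off drug partly because many subjects never came off drug. The more responders stay in the OLE, the lower the printed off-drug percentage becomes, whatever happens to the subjects who are actually followed.

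**Working it through.** **No figure to reproduce.** The documents state no follow-up event percentage and no OLE share. The check is denominator arithmetic with one input from the documents and one assumption.

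**Inputs**
- N = 50, the planned enrolment (SAP 3.2), taken as the size of the Safety Analysis Set.
- f = share of the Safety Analysis Set still on OLE drug at the cut-off. Not in the documents; assumed range 0.3 to 0.7.
- x = number of subjects with at least one follow-up event. Illustrative value 5.

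**Formulas**
- Followed subjects: n = N(1 - f)
- Printed percentage under SAP 7.1.7: x/N
- Percentage among followed subjects: x/[N(1 - f)]
- Ratio of printed to followed: 1 - f, so the relative understatement is f and does not depend on x.

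**Results for x = 5, N = 50**

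| f (assumed) | Followed n | Printed | Among followed | Relative understatement |
|---|---|---|---|---|
| 0.3 | 35 | 5/50 = 10.0% | 5/35 = 14.3% | 30% |
| 0.5 | 25 | 5/50 = 10.0% | 5/25 = 20.0% | 50% |
| 0.7 | 15 | 5/50 = 10.0% | 5/15 = 33.3% | 70% |

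**Still on drug is not the same as ever entered.** Subjects who leave the OLE do go into follow-up. If a share e enters the OLE and a fraction d of the entrants has stopped by the cut-off, then f = e(1 - d). With e = 0.6 assumed:
- d = 0: f = 0.60, n = 20, 5/20 = 25.0%
- d = 0.1: f = 0.54, n = 23, 5/23 = 21.7%
- d = 0.2: f = 0.48, n = 26, 5/26 = 19.2%
- d = 0.3: f = 0.42, n = 29, 5/29 = 17.2%

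**Incomplete follow-up.** A subject last dosed at Week 10 finishes follow-up at about Week 10 + 12 = Week 22, while the analysis can follow the last subject's Week 12. Some subjects who have entered follow-up will therefore be only partly observed. The (1 - f) factor does not include this.

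**The case against.** The strongest reply is that SAP 7.1.7 never writes out a division. Naming the Safety Analysis Set may only identify the source population, and the rule on column headings does not say that every period-specific percentage must use that N. This is right as far as it goes: the denominator is inferred. But the SAP names one set for both periods, requires its size in the heading, and defines no set of followed subjects. A programmer following the text has no other denominator to use.

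The second reply is that little depends on it. Safety is descriptive with no testing (SAP Section 7), counts are printed, and all events are listed. The primary safety objective concerns the 12 weeks of induction, for which all treated subjects are at risk and the Safety Analysis Set is correct. All of this stands and limits the point to the follow-up percentages. It also stands that f is unknown, so the size can only be shown as a range.

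Two stronger readings are tempting, and the documents do not support them:

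- *OLE exposure is diluted too.* SAP 5.3.1 says that "infusions received for the IP and OLE will be summarized using descriptive statistics for the Safety Analysis Set", and a reader might infer that mean OLE infusions are averaged over subjects who never entered. The full sentence also covers total duration of exposure and can be read as cumulative exposure over both periods, for which the Safety Analysis Set is right. Dilution would need zeros entered for non-entrants, which the SAP does not call for; SAP 4.3 generally leaves missing data unimputed in descriptive statistics.
- *OLE events are pooled with induction events.* SAP 7.1.7 gives no end to the treatment period, so a reader might infer a single mixed column. But SAP 5.3.1 sets an induction end for exposure, SAP 4.2.5 defines an OLE set reported by randomised group, and SAP Section 9 defers the complete OLE analysis to a separate plan. This is mainly missing detail, not a planned pooling.

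**Conclusion.** The point holds for the post-treatment and follow-up adverse event percentages at the primary analysis. Followed as written, SAP 7.1.7 understates them by the relative fraction f: 30% at f = 0.3, 50% at f = 0.5 and 70% at f = 0.7.

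This rests on three things: that the Safety Analysis Set N is the divisor, which is inferred from SAP 4.1, 4.2 and 7.1.7 together; that everyone not on OLE drug at the cut-off is in or through follow-up; and the assumed range for f. If nobody is still on OLE drug at the cut-off, f = 0 and the two percentages agree.

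A reader might take this as a flaw in the trial's main safety result, or equate f with everyone who ever entered the OLE. Neither follows. The induction proportions keep a correct denominator, counts and listings are untouched, no test is involved, and subjects who leave the OLE rejoin the group that is followed. It is a modest defect in a descriptive table, worth correcting because the correction is nearly free.

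**What to change.** In SAP 7.1.7, for the post-treatment adverse event summaries and the follow-up table by system organ class and preferred term:

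1. Use as denominator the Safety Analysis Set subjects who entered post-dosing follow-up by the cut-off, that is, those who have had their last dose and are not continuing in the OLE.
2. Print that n in the column heading.
3. State the day on which the post-treatment period starts, so that events and subjects are assigned by the same rule.
4. Keep the full Safety Analysis Set for induction adverse events.

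As a consistency point only, any OLE-only exposure or adverse event table should use the OLE analysis set already defined in SAP 4.2.5.

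The cost is a few sentences in the SAP and a different denominator in tables already planned; no new data are needed and conduct does not change. The downside is that follow-up percentages will rise and rest on a smaller n, so they will be less precise. Footnoting how many of the followed subjects had completed the 12 weeks by the cut-off would help the reader judge them.
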